### 12.1.2. Secondary Endpoint

The rate of bleeding, based upon the Bleeding Academic Research Consortium (BARC) classification (types 2, 3 and 5), between 3 and 15 month expressed as the proportion of subjects who experience bleeding between 3 and 15 months among all subjects who either experience bleeding between 3 and 15 months or survive free of bleeding for at least 425 days (analysis excludes subjects on chronic anticoagulants).

#### 12.1.2.1. Hypothesis

The null hypothesis that the difference of bleeding rates between test group and historical control group is greater than or equal to zero will be tested against the alternative hypothesis that the difference between test group and historical control group is less than zero:

$$H_0: P_{MB-3M} - P_{MB-12M} \geq 0$$

$$H_1: P_{MB-3M} - P_{MB-12M} < 0$$

where  $P_{MB-3M}$  and  $P_{MB-12M}$  are the 3 to 15-month bleeding rates for the 3-month DAPT test group and the 12-month DAPT historical control group, respectively.

The historical control group for the hypothesis testing for bleeding is only from HCRI DAPT Study minus TAXUS. A second propensity score model will be developed based on the same set of covariates used in the propensity score model for the death/MI co-primary endpoint. The second propensity score model using quintile adjustment for the bleeding will be used to test the one-sided hypothesis of superiority of the test group compared to historical control group.

#### 12.1.2.2. Sample Size

The expected rate of 4% for 3 to 15 month bleeding rate in subjects at high risk for bleeding for control group is estimated from the BSC PROMUS subjects enrolled in the HCRI DAPT study. The expected rate for 3 to 15 month bleeding rate in subjects at high risk for bleeding for test group is set to be 2.19%. In the control group, there are approximately 1,240 historical -limus DES high risk for bleeding subjects available from HCRI DAPT Study minus TAXUS. The number of evaluable subjects available in the test group required in the propensity score model for the death/MI co-primary endpoint and the ARC ST co-primary endpoint is 1,650. Given the number of subjects of 1,650 in the test group and 1,240 in the historical control group, the unadjusted power is 80%. Assuming that the dropout rate due to the ineligibility between 0 and 3 months for the test group is 15% and the expected attrition rate between 3 and 15 months is 3%, the study needs to enroll 2,000 subjects for the test group.

The enrollment may be terminated earlier if the observed dropout rate between 0 and 3 months is projected to be less than 15%. Enrollment may be continued beyond 2,000 subjects (up to a maximum of 2,250 subjects) if the observed dropout rate in 0 to 3 months is projected to be >15%.

The sample size calculation is based on unequal allocation using 2-group chi-square test compare two proportions using nQuery Advisor® Version 5.0.

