
Secondary Endpoint (Bleeding) Sample Size Parameters
	
 
• Expected 3 to 15 month bleeding rate from 12-month DAPT (control) = 4%a
 
• Expected 3 to 15 month bleeding rate from 3-month DAPT (test) = 2.19%
 
• Test significance level = 0.025 (1-sided)
 
• Control subjects are historical -limus DES treated subjects at high risk for bleeding obtained from the HCRI DAPT study, number of available historical control subjects is approximately 1,240
 
• Number of evaluable test subjects in the propensity score model is 1,650 (including additional 10% subjects accounting for model variability)
 
• Power = 80% using chi-square test (unadjusted power for 1,240 vs 1,650)
 
• Expected drop out rate due to ineligibility for 3 month DAPT in 0 to 3 months = 15%
 
• Expected attrition rate in 3 to 15 months = 3%
 
• N = 2,000b subjects enrollment
 
 
aThe expected rate for 3 to 15-month bleeding rate is estimated from the BSC PROMUS subjects at high risk for bleeding enrolled in the HCRI DAPT study (10/253).
 
bThe enrollment may be terminated early if the observed dropout rate in 0 to 3 months is projected to be <15%.

Study Success Criteria
	
The study will be considered a success if both the co-primary endpoints of death/MI and ARC definite/probable stent thrombosis are met.

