**9.3. Exclusion Criteria**

Subjects who meet any one of the following criteria (Table 9.3-1) will be excluded from this clinical investigation.

	
 
1. Subject who is taking (or is planning to take) chronic or lifelong anticoagulation within 15 months following index procedure.
 
2. Subject with an indication for the index procedure of acute ST elevation MI (STEMI)
 
3. Subject with an indication for the index procedure of Non ST elevation MI (NSTEMI), based on the 3rd Universal MI definition (1)
 
4. Subject with treatment with another coronary stent, other than SYNERGY, during the index procedure
 
5. Subject with planned staged procedures. (Note: Planned staged procedures are allowed if performed within 7 days and with only SYNERGY stents).
 
6. Subject has a known allergy to contrast (that cannot be adequately pre-medicated), the SYNERGY stent system or protocol-required concomitant medications (e.g., everolimus or structurally related compounds, polymer or individual components, all P2Y12 inhibitors and aspirin)
 
7. Subject with implantation of a drug-eluting stent within 9 months prior to index procedure
 
8. Subject previously treated at any time with intravascular brachytherapy
 
9. Subject has an active peptic ulcer or active gastrointestinal (GI) bleeding
 
10. Subject is participating in an investigational drug or device clinical trial that has not reached its primary endpoint (Note: registry, observational, data collection studies are not exclusionary)
 
11. Subject intends to participate in an investigational drug or device clinical trial within 15 months following the index procedure (Note: registry, observational, data collection studies are not exclusionary)
 

--	---

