**11.10.1.1. Eligible for Discontinuation of P2Y12 Inhibitor at 3 Months**

Subjects are eligible for discontinuation of P2Y12 inhibitor at 3 months if they meet both of the following criteria:

- Subject was treated with 3 months of P2Y12 inhibitor/aspirin post index procedure. (Subjects enrolled under a prior version of the protocol who were on chronic anticoagulation between 0-3 months are eligible if they were also taking P2Y12 inhibitor or P2Y12 inhibitor/aspirin between 0-3 months).
- Subject was free from events (stroke, MI, PCI, CABG, and stent thrombosis) between the index procedure and the 3-month visit

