### 12.2.1. Analysis Sets

For the EVOLVE Short DAPT Study, a subject is considered enrolled once an informed consent form has been signed and the subject has received at least one commercial SYNERGY stent. Enrolled subjects must meet all inclusion and no exclusion criteria. The analysis set for the test group includes enrolled subjects who meet criteria for discontinuation of P2Y12 inhibitor and who discontinue P2Y12 inhibitor at 3 months. The analysis set will be used as the test group in the propensity score model.

For the death/MI co-primary endpoint analysis, the EVOLVE Short DAPT-like high risk for bleeding subjects will be extracted from HCRI DAPT, PE+ PAS, and PE PROVE studies to form the historical control group. For the secondary bleeding endpoint analysis, the EVOLVE Short DAPT-like high risk for bleeding subjects will be extracted from HCRI DAPT study only to form the historical control group. Bleeding events were not adjudicated by the CEC in the PE+PAS or the PE-PROVE study.

The EVOLVE Short DAPT-like subjects are defined as subjects who meet the EVOLVE Short DAPT Study inclusion criteria and do not meet any of the following exclusion criteria at the time of the index procedure:

- indication for the index procedure of acute ST elevation MI (STEMI) or Non ST elevation MI (NSTEMI),
- previously treated with intravascular brachytherapy,
- left main target lesion,

- more than 3 lesions treated,
- more than 2 vessels treated,
- bifurcations,
- in-stent restenosis,
- saphenous vein graft,
- TIMI flow 0 (total occlusion) or TIMI flow 1 prior to guide wire crossing, and
- thrombus or possible thrombus present in the target vessel (by visual estimate).

The high risk for bleeding subject set is defined as a set of subjects who meets one or more of the following criteria at the time of enrollment:  $\geq 75$  years of age and, in the opinion of the investigator, the risk of bleeding associated with  $>3$  months of DAPT outweighs the benefit, chronic or lifelong anticoagulation therapy, history of major bleeding (severe/life threatening or moderate bleeding based on the GUSTO classification) within 12 months of the index procedure, stroke (ischemic and hemorrhagic), or renal insufficiency (creatinine  $\geq 2.0$  mg/dl) or failure (dialysis dependent), and platelet count  $\leq 100,000$   $\mu\text{L}$ .

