#### Propensity Scores Modeling Approach

To avoid potential bias, an independent propensity score model team, who is blinded to the outcome data, will develop two propensity score models based on the same set of covariates with three historical studies used in the first model and one historical study used in the second model.

The first propensity score model for the death/MI co-primary endpoint will be based on the analysis set for the test group from the EVOLVE Short DAPT Study and the EVOLVE Short DAPT-like high risk for bleeding subjects for the control group from HCRI DAPT, PE+ PAS, and PE PROVE studies.

The second propensity score model for bleeding will be based on the analysis set for the test group from the EVOLVE Short DAPT Study and the EVOLVE Short DAPT-like high risk for bleeding subjects for the control group from HCRI DAPT study. Subjects who were on long-term anticoagulation therapy and who were anticipated to still be on an anticoagulant at the time of randomization were not eligible for enrollment in HCRI DAPT study. In order to make a like-

to-like comparison between test and control groups, subjects with a need for chronic or lifelong anticoagulation therapy in the test group will be excluded from the second propensity score model for the bleeding secondary endpoint.

The independent propensity score model team will select the appropriate propensity score models prior to the endpoint analyses and file the propensity score baseline covariate modeling as an IDE supplement. The selected propensity score models will be delivered to an independent outcome reporting team for the endpoint analyses. The independent outcome reporting team will use these propensity score models to test the hypotheses of the test group compared to the control group and to compare other clinical outcomes between the test group and control group.

The missing data for the propensity score model covariates will be imputed. The within-study median value of the non-missing covariate for the subjects used in the propensity score model will be used as the imputed value for the missing continuous covariate. The within-study mode value of the non-missing covariate for the subjects used in the propensity score model will be used as the imputed value for the missing discrete covariate.

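### The 80% bleeding power is computed on 1,650 test subjects, but chronically anticoagulated subjects are removed from that analysis with no allowance in the sample size

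*Combined protocol and SAP*

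**What the plan says.** Section 12.1.2.2 takes its test-group number from the requirement for death/MI and stent thrombosis, and then states: "Given the number of subjects of 1,650 in the test group and 1,240 in the historical control group, the unadjusted power is 80" per cent. The synopsis row on bleeding sample size repeats it: "Power = 80% using chi-square test (unadjusted power for 1,240 vs 1,650".

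The bleeding analysis is run on a narrower group. Section 12.1.2 says of this endpoint: "analysis excludes subjects on chronic anticoagulants". Section 12.2.2, under the propensity score approach, says: "subjects with a need for chronic or lifelong anticoagulation therapy in the test group will be excluded from the second propensity score model". That exclusion is stated for the bleeding model and not for the death/MI model.

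Anticoagulated subjects can be in the test group. Section 11.10.1.1 says: "Subjects enrolled under a prior version of the protocol who were on chronic anticoagulation between 0-3 months are eligible", provided they also took a P2Y12 inhibitor, with or without aspirin, in those months. Section 12.2.1 builds the test set from subjects who qualify for discontinuation and then stop: "The analysis set for the test group includes enrolled subjects who meet criteria for discontinuation of P2Y12 inhibitor". The current exclusion criteria (section 9.3, item 1) shut out new ones: "Subject who is taking (or is planning to take) chronic or lifelong anticoagulation within 15 months following index procedure". Section 28.2 gives the reason for that change: anticoagulated patients had been enrolled in larger numbers than foreseen. It gives no count.

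On enrolment, section 12.1.2.2 allows for 15% ineligibility by 3 months and 3% later attrition. The one route to a larger study is tied to dropout: "Enrollment may be continued beyond 2,000 subjects (up to a maximum of 2,250 subjects) if the observed dropout rate" between 0 and 3 months is projected to exceed 15%.

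**The concern.** The power statement and the analysis refer to different groups. The 1,650 counts every evaluable test subject, while the bleeding comparison uses only those not on chronic anticoagulation. If the study reaches its planned evaluable total, the bleeding analysis will have fewer test subjects than the power calculation assumes, and nothing in the sample size section makes up the difference.

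Bleeding is the only secondary endpoint and carries a formal one-sided superiority test. If superiority is not shown, readers will judge that result against 80% power, which the analysed group may not have had. The co-primary conclusions are not touched, because study success depends only on death/MI and stent thrombosis.

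**Working it through.** **Inputs** (section 12.1.2.2 and the synopsis bleeding row): control rate p₂ = 4%; test rate p₁ = 2.19%; control n₂ = 1,240; test n₁ = 1,650; one-sided α = 0.025 (z = 1.960); two-group chi-square test; 0 to 3 month dropout 15%; 3 to 15 month attrition 3%.

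**Formula** (pooled variance under the null, no continuity correction):

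- p̄ = (n₁p₁ + n₂p₂)/(n₁ + n₂)
- SE₀ = √[p̄(1 − p̄)(1/n₁ + 1/n₂)]
- SE₁ = √[p₁(1 − p₁)/n₁ + p₂(1 − p₂)/n₂]
- power = Φ[(p₂ − p₁ − 1.960 × SE₀)/SE₁]

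**Step 1: the plan's own figure.** With n₁ = 1,650: p̄ = 0.02967, SE₀ = 0.006377, SE₁ = 0.006629. Then (0.0181 − 1.960 × 0.006377)/0.006629 = 0.845 and Φ(0.845) = 80.1%. The stated 80% is right for its inputs.

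**Step 2: is there slack?** 2,000 × 0.85 × 0.97 = 1,649 evaluable subjects, so the two stated losses use up the planned enrolment. The 1,650 already contains the 10% allowance for model variability (1,500 × 1.1), and the bleeding power uses all of it, so that allowance is not a reserve. By the same formula, unrounded power of 80.0% needs at least 1,642 test subjects, 8 fewer than 1,650.

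**Step 3: remove the anticoagulated subjects.** Their share of the 1,650 is not in the documents; the shares below are assumptions.

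| Assumed share removed | Test subjects left | Unadjusted power v 1,240 |
|---|---|---|
| 0% | 1,650 | 80.1% |
| 3.1% (51 subjects) | 1,599 | 79.5% |
| 5% | 1,568 | 79.1% |
| 10% | 1,485 | 78.0% |
| 20% | 1,320 | 75.5% |
| 30% | 1,155 | 72.2% |

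The 3.1% row is the largest loss at which the power still rounds to 80%.

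**Step 4: sensitivity.**

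- The 4% is a rounding of 10/253 = 3.95%. Using 10/253 at the full 1,650 gives 78.3%, so at small shares the loss is no larger than the effect of that rounding.
- Section 12.1.2.3 tests with a confidence bound from a normal approximation. Using the unpooled SE₁ throughout and ignoring the quintile strata, power is 77.9% at 1,650, 76.6% at 1,485 and 75.0% at 1,320. On that basis the exclusion itself costs 1.3 points at a 10% share and 2.9 points at 20%.

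**Step 5: would the extension cover it?** Enrolling 2,250 with dropout still at 15% would give 2,250 × 0.85 × 0.97 = 1,855 evaluable, and about 11% could then be removed while keeping 1,642. But the plan goes beyond 2,000 only when dropout is above 15%, so the extra subjects replace that loss. Enrolment may also stop early if dropout is below 15%. Neither rule counts subjects who are not anticoagulated.

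**The case against.** The strongest reply is that nothing is miscalculated. The sentence is conditional on 1,650 v 1,240, the power is labelled unadjusted, and 80% follows from those inputs. This stands as far as it goes. The fault is a mismatch of populations, not a slip in the calculation. But the word unadjusted refers to the propensity score adjustment. It does not tell the reader that some of the 1,650 will not be in the analysis.

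A second reply is that the effect is small beside the softness of the inputs. This largely stands. The 10 events in 253 behind the 4% have an exact 95% interval of about 1.9% to 7.1%. The control number is itself approximate: 1,180 controls in place of 1,240 would also give 79.1%. The 2.19% is set without a source. With 10% removed, a test rate of 2.15% in place of 2.19% would bring power back to 80%.

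Third, the size cannot be known. The revision history says only that anticoagulated enrolment ran above expectation; new cases are barred, and only those who qualified for and stopped the P2Y12 inhibitor count. This stands too: the 20% and 30% rows have no anchor in the documents and show only how the loss would grow.

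None of these replies points to a place in the plan where the bleeding number is adjusted for the exclusion.

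**Conclusion.** The concern holds, as a minor point. The stated bleeding power belongs to the co-primary evaluable group and not to the group in which bleeding will be analysed. If the evaluable total is about 1,650 as planned, and any anticoagulated subjects are in the test set, the bleeding analysis is smaller than stated and the plan makes no allowance for it.

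The mismatch is clear from the text; the size of the loss is not. At assumed shares up to 10% the power stays within about 2 points of 80%, and larger losses need shares that the documents neither support nor rule out. The loss is limited to subjects enrolled before anticoagulation became an exclusion. These figures rest on the plan's own rates, 1,240 controls, and the unadjusted chi-square calculation. If the evaluable total ends up well above 1,650, the shortfall shrinks or disappears.

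**What to change.** In section 12.1.2.2 and in the synopsis row on bleeding sample size, replace 1,650 with the expected number of evaluable test subjects not on chronic anticoagulation, and restate the unadjusted power at that number against 1,240 controls. For example: *Given approximately [N] evaluable test subjects not on chronic anticoagulation and 1,240 historical control subjects, the unadjusted power is [x]%.* The sponsor can take N from the count of anticoagulated subjects already enrolled, since no more can join under the current version.

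The cost is two figures restated in two places. Enrolment, endpoint, test and significance level stay as they are. The stated power may come out slightly lower.

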### 12.1.2.3. Statistical Methods

The second propensity score model with quintile adjustment will be used to address baseline imbalance between the test group and the historical control group. The null hypothesis will be tested against alternative hypothesis using the propensity score quintile adjusted secondary endpoint of bleeding for testing superiority between the test group and the historical control group.

The adjusted between-group difference estimate ( $\bar{d}$ ) and the standard error ( $SE(\bar{d})$ ) of the adjusted between-group difference will be used to construct the 97.5% upper confidence bound of the adjusted between-group difference using normal approximation to binomial. If the 97.5% upper confidence bound is less than zero, the null hypothesis will be rejected for the secondary endpoint of bleeding and the test group will be concluded to be superior to historical control group.

## 12.2. *General Statistical Methods*

All statistical analyses will be performed using the SAS System software, version 9.3 or later (Copyright© 2002-2010 by SAS Institute Inc., Cary, North Carolina, USA. All rights reserved).

All statistical analyses will be conducted according to applicable Standard Operating Procedures, Work Instructions, and the study-specific Statistical Analysis Plan.

### 12.2.1. Analysis Sets

For the EVOLVE Short DAPT Study, a subject is considered enrolled once an informed consent form has been signed and the subject has received at least one commercial SYNERGY stent. Enrolled subjects must meet all inclusion and no exclusion criteria. The analysis set for the test group includes enrolled subjects who meet criteria for discontinuation of P2Y12 inhibitor and who discontinue P2Y12 inhibitor at 3 months. The analysis set will be used as the test group in the propensity score model.

For the death/MI co-primary endpoint analysis, the EVOLVE Short DAPT-like high risk for bleeding subjects will be extracted from HCRI DAPT, PE+ PAS, and PE PROVE studies to form the historical control group. For the secondary bleeding endpoint analysis, the EVOLVE Short DAPT-like high risk for bleeding subjects will be extracted from HCRI DAPT study only to form the historical control group. Bleeding events were not adjudicated by the CEC in the PE+PAS or the PE-PROVE study.

The EVOLVE Short DAPT-like subjects are defined as subjects who meet the EVOLVE Short DAPT Study inclusion criteria and do not meet any of the following exclusion criteria at the time of the index procedure:

- indication for the index procedure of acute ST elevation MI (STEMI) or Non ST elevation MI (NSTEMI),
- previously treated with intravascular brachytherapy,
- left main target lesion,

- more than 3 lesions treated,
- more than 2 vessels treated,
- bifurcations,
- in-stent restenosis,
- saphenous vein graft,
- TIMI flow 0 (total occlusion) or TIMI flow 1 prior to guide wire crossing, and
- thrombus or possible thrombus present in the target vessel (by visual estimate).

The high risk for bleeding subject set is defined as a set of subjects who meets one or more of the following criteria at the time of enrollment:  $\geq 75$  years of age and, in the opinion of the investigator, the risk of bleeding associated with  $>3$  months of DAPT outweighs the benefit, chronic or lifelong anticoagulation therapy, history of major bleeding (severe/life threatening or moderate bleeding based on the GUSTO classification) within 12 months of the index procedure, stroke (ischemic and hemorrhagic), or renal insufficiency (creatinine  $\geq 2.0$  mg/dl) or failure (dialysis dependent), and platelet count  $\leq 100,000$   $\mu\text{L}$ .

